#### **1.4.2.4 Planned measures for monitoring the risks**

Patients will be evaluated with functional, imaging and systemic tests to identify any possible adverse event. Specifically, any signs of intraocular inflammation will be assessed by slitlamp examination of anterior chamber, vitreous and posterior segment of the eye, to identify occurrence of flare or cells in the anterior chamber, deposits of material in the corneal endothelium, deposits on the anterior capsule of the crystalline lens, any signs of vitreous haze, vitreous cells, vitreous snowbanks/snowballs, signs of intraretinal edema or retinal thickening, signs of perivascular inflammation e.g. vessel walls sheathing, signs of incipient retinitis or intraretinal haemorrhages.

Spectral domain optical coherence tomography (SD-OCT) will be used to evaluate any possible occurrence of intraretinal cystic edema or perivascular reaction. The same imaging modality will be used to evaluate early signs of cell toxicity (e.g. increased ellipsoid zone disruption, granular appearance of outer retinal layers, increase in intraretinal foci predominantly located in the outer nuclear layers).

Additionally, a systemic evaluation will be performed at the time-points specified in the flow charts, to assess any possible systemic reaction. This will include body weight, blood pressure, heart rate with Electrocardiogram (ECG), full safety lab. The required assessments will be adapted according to the pre-clinical trial results. All these evaluations will have to be reported immediately for evaluating any possible safety issue related to the drug or to inflammatory response.

In the trial design a sentinel approach will be used in the SRD part, according to EMA and ICH guidelines (EMA/CHMP/SWP/28367/07 Rev.1; EMA/CHMP/ICH/731268/1998): for each cohort the first patient will be dosed and monitored to exclude acute AEs, before dosing the other patients of the same cohort (see Section [3.1](#)). Moreover, the duration of the observation will reflect the expected human pharmacokinetics (PK) of BI 764524, with a follow-up for all patients up to 98 days, with appropriate ophthalmologic and systemic evaluations (see Section [3.1](#)).

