##### SRD part:

In the SRD part, the starting dose is [REDACTED]. The other provisional dose level is [REDACTED], and the maximum planned dose is [REDACTED]. For each cohort, a single patient will be dosed on day 1, and the dosing investigator, coordinating investigator and 2 representatives of the sponsor who are involved in the trial will carefully evaluate all available systemic (i.e. physical examinations, safety lab parameters, ECG and AEs) and ophthalmologic (i.e. as defined in Section 5.2.1) safety data until day 4. If this patient neither has experienced an ophthalmologic nor a systemic serious adverse event, the remaining 2 patients will be dosed. Written minutes of this assessment are being distributed to all investigators participating in this trial.

For any dose-escalation cohort, at least 3 evaluable patients will be required. Each cohort will consist of newly enrolled patients.

A Safety Monitoring Committee (SMC, see Section 8.7) will decide on the next dose level to be investigated and on the size of the next cohort based on occurrence of DLEs and on additional information (systemic PK and patient profiles). Systemic PK data from preceding cohorts (not from the ongoing cohort) will be available for evaluation. First SMC meeting will take decision based on safety data only. Refer to figure 3.1:1 (SRD) and figure 3.1:2 (MD) for a schematic representation of the dose escalation.

A Bayesian logistic regression model (BLRM), based on a weekly informative prior distribution, and employing the escalation with overdose control (EWOC) principle (see Section 7) will be used for guiding the dose escalation [R13-4803]. After all patients in a cohort have either experienced a DLE or have been observed for at least the 7 days evaluation period without experiencing a DLE (I.e. 7 days after drug administration, until visit 4, will be evaluated per patient), the BLRM will be updated with the newly accumulated data. The overdose risk will then be calculated for each dose, and escalation will be permitted to all planned doses which fulfil the EWOC criterion and the respective escalation rule.

The BLRM provides estimates for the probability of observing a DLE for each planned dose. Dose escalation will be permitted to the next planned dose which fulfils the EWOC criterion. Note that this may also result in repeating the current dose level, or in going down to a lower dose level again.

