If DLEs are observed in the first two consecutive patients of a previously untested dose level, subsequent enrolment to that cohort will be stopped.

The maximum feasible dose (MFD) is considered as reached if at least 6 patients have been evaluated at a dose level which is the model's recommendation for the next dose cohort. Note the MFD will likely be the highest feasible dose, [REDACTED], rather than the highest tolerable dose in strict sense. The MD part of the study would only start if the highest dose ([REDACTED]) is tolerated.

- After the DLE period (7 days after drug administration) is over for the last patient in the SRD part, all available trial data will be analyzed and a decision is made whether to proceed to the MD part or not. Before starting the MD part, regulatory authorities and institutional review boards (IRBs) / independent ethics committees (IECs) will be informed of the internal results of the SRD part.

[figure not shown]

Figure 3.1: 1 Schematic representation of the dose escalation process in the SRD part of the trial

MD part:

The MD part will consist of one dose cohort (N=20 on dose + 10 sham injection). The highest dose [REDACTED] if established as safe and tolerable during the SRD part will be used in the MD part after the SRD part has been completed. Patients that had received a dose in the SRD part of the trial will not be included. Patients will be randomized to receive either active treatment or sham injection.

In the MD cohort, patients will receive three consecutive doses/sham injection over a 3-month period (dosing every 4 weeks). The SMC will meet regularly to review the safety data.

In all patients included in the MD part of the trial, safety and early biological response will be studied up to 98 days after the last injection.

[figure not shown]

Figure 3.1: 2                      Schematic representation of the dosing in the MD part of the trial

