### 3.3.4.3 Discontinuation of the trial by the sponsor

Boehringer Ingelheim reserves the right to discontinue the trial overall or at a particular trial site at any time for any of the following reasons:

1. Failure to meet expected enrolment goals overall or at a particular trial site
2. Emergence of any efficacy/safety information invalidating the earlier positive benefit-risk assessment that could significantly affect the continuation of the trial
3. Deviation from GCP, the CTP, or the contract impairing the appropriate conduct of the trial.

For the following scenario further enrolment and entering into the trial will be interrupted by the sponsor once the sponsor becomes aware (i.e. stopping rule):

- A single serious adverse reaction (i.e. a single serious adverse event) or two severe adverse reactions in two different patients (regardless of the system organ class) confirmed by both the investigator and sponsor as having a reasonable causal relationship to the IMP administration.

The investigator / trial site will be reimbursed for reasonable expenses incurred in case of trial termination (except in case of the third reason).

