## 5.2 ASSESSMENT OF SAFETY

### 5.2.1 Dose limiting event

A DLE is defined as the occurrence of any of the following events in the study eye within the evaluation period (7 days after drug administration):

- Development of sterile endophthalmitis and/or sterile inflammation of the vitreous of grade 3+ according to the NEI Grading of vitreous haze, and anterior chamber cells of 3+ according to the Standardization of Uveitis Nomenclature (SUN) working group (WG) grading scheme (see Table 5.2.1: 1 below) and a duration of 5 or more days between day 1 and day 8
- Visual loss of more than 15 letters at any given time-point
- Persistent IOP over 30 mmHg for 3 days
- Signs of vascular occlusion in a 1st (the main branch) or 2nd degree (the vessel after the first bifurcation of the main branch) retinal vessel, including peripheral retinal hemorrhages in the area supplied by the occluded vessel (hemorrhage of the macula would not be included as this is a symptom of the disease).

Table 5.2.1: 1 The SUN Working Group Grading Scheme for Anterior Chamber Cells ([R18-1136](#))

Grade	Cells in Field 
0	<0
0.5+	1-5
1+	6-15
2+	16-25
3+	26-50
4+	>50

 Field size is a 1 mm by 1 mm slit beam.

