###### **5.2.7.1.2 Serious adverse event**

A serious adverse event (SAE) is defined as any AE which fulfils at least one of the following criteria:

- Results in death
- Is life-threatening, which refers to an event in which the patient was at risk of death at the time of the event; it does not refer to an event that hypothetically might have caused death if more severe,
- Requires inpatient hospitalisation
- Requires prolongation of existing hospitalisation
- Results in persistent or significant disability or incapacity
- Is a congenital anomaly/birth defect

- Is deemed serious for any other reason if it is an important medical event when based upon appropriate medical judgment which may jeopardise the patient and may require medical or surgical intervention to prevent one of the other outcomes listed in the above definitions. Examples of such events are intensive treatment in an emergency room or at home for allergic bronchospasm, blood dyscrasias or convulsions that do not result in hospitalisation or development of dependency or abuse

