## **6.2.2 Treatment period(s)**

For the SRD part, masking is not required for the IVT injection preparation or administration. For the MD part, IVT injection will be prepared by the unmasked pharmacist (qualified person). For the MD part, an unmasked injector with no other involvement in the trial will administer either active or sham injection according to the treatment assigned by IRT. IVT injections must be carried out according to medical standards and applicable guidelines by a qualified physician experienced in administering IVT injections and will be done as part of drug administration visit procedures (Visit 2 for SRD part and Visits 2, 3 and 4 for MD part) after the other ophthalmologic assessments in the [Flow Chart I](#) and [Flow Chart II](#) have been performed (please see Section [4.1](#) for details).

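### SRD patients 2 and 3 share one Day 4 release gate with no stated spacing, so in a cohort of exactly 3 the two-DLE stop spares patient 3 only if that patient happens to be dosed late enough

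*Protocol*

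**What the plan says.** **Release.** Protocol Section 3.1 doses one patient per cohort on Day 1. The dosing investigator, the coordinating investigator and two sponsor representatives then review systemic data and the Section 5.2.1 eye data up to Day 4. The release condition is: "If this patient neither has experienced an ophthalmologic nor a systemic serious adverse event, the remaining 2 patients will be dosed". Section 1.4.2.4 likewise separates only the first patient, who is observed "before dosing the other patients of the same cohort".

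**Stop.** Section 3.1 also states: "If DLEs are observed in the first two consecutive patients of a previously untested dose level, subsequent enrolment to that cohort will be stopped".

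**DLE definition.** Section 5.2.1 counts events within 7 days of dosing. The inflammation criterion requires the stated grades "and a duration of 5 or more days between day 1 and day 8". The pressure criterion is "Persistent IOP over 30 mmHg for 3 days". Loss of more than 15 letters and retinal vessel occlusion have no duration requirement.

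**Status of a DLE.** Section 5.2.7.1.4 makes every DLE an adverse event of special interest (AESI), reportable within 24 hours under Section 5.2.7.2.2. It does not make every DLE serious.

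**The concern.** The release gate and the stop use different events and different clocks. The gate asks about a serious adverse event in patient 1 by Day 4. The stop asks about DLEs in patients 1 and 2, each judged over 7 days. A non-serious DLE in patient 1, or one that cannot yet be confirmed, leaves the gate open for both remaining patients.

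If patients 2 and 3 are then dosed close together, the stop has nobody left to protect in a 3-patient cohort. At stake is one further patient exposed, in a first-in-human trial, to a dose that has just produced DLEs in both patients before them.

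**Working it through.** **1. Timeline on nominal days (Section 3.1, Section 5.2.1, Flow Chart I).**

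| Event | Trial day |
|---|---|
| Patient 1 dosed | 1 |
| Review; patients 2 and 3 may both be dosed | from 4 |
| Patient 1's DLE window closes | 8 |
| Patient 2's DLE window closes, at the earliest | 4 + 7 = 11 |

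Nothing visible requires patient 3 to wait for Day 8 or Day 11.

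**2. Can patient 1's DLE still be pending at Day 4?** For inflammation, yes: 5 days cannot have elapsed. For pressure, Day 4 is the first scheduled reading after the injection, because the Day 1 injection comes "after the other ophthalmologic assessments in the" flow chart (Section 6.2.2). Unscheduled visits (Section 6.2.3) could settle the pressure criterion by Day 4, but not the 5-day one.

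**3. Does the dose-escalation model protect patient 3?** No. Section 3.1 updates it only once every patient in the cohort has had a DLE or completed 7 days.

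**4. Upper bound on the size.** With a true DLE rate p and independent patients, the probability that patients 1 and 2 both have a DLE is p².

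The dose headings of Table 10.2:2 are redacted. I take its third column as the top dose, for two reasons: Table 4.1.2:1 plans three levels, and Table 10.2:3 shows 0% overdosing in scenario 5 although column 4 there is 0.500.

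| Scenario | p (column 3) | p² |
|---|---|---|
| 1 Prior medians | 0.054 | 0.3% |
| 2 Prior means | 0.153 | 2.3% |
| 3 High toxicity | 0.280 | 7.8% |
| 4 Low toxicity | 0.010 | 0.01% |
| 5 Non-logistic | 0.200 | 4.0% |
| 6 Low then high | 0.400 | 16% |

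**5. Cross-check with the protocol's prior (Section 7.1).** Doses 0.5, 1 and 2.5 are readable in Table 7.1:2. The reference dose is redacted. A value of 3 returns component 1's stated medians of 0.02 and 0.10, so I use it.

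- Reproduction of the prior: mean DLE rates 0.091, 0.122 and 0.205, against 0.091, 0.121 and 0.202 in Table 7.1:2.
- Reproduction after 0/3 at 0.5 and 0/3 at 1: overdose probability at 2.5 of 0.121, against 0.126 in Table 10.2:1, scenario 3.
- From that same posterior, the expected value of p² at 2.5 is 0.030, or 3.0%.
- If two DLEs in two patients then occurred at 2.5, the overdose probability would be 0.784 against the limit of 0.25, and patient 3's predicted DLE risk would be about 45%.

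So the event is uncommon, but when it occurs the protocol's own model would judge the dose unacceptable for patient 3.

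**The case against.** The strongest reply is that the two rules are compatible. The release sentence does not say that patients 2 and 3 are dosed on the same day. Section 4.1.3 has patients enter as they become available, and once two DLEs are seen the stop applies. That stands. A reader might infer that the plan requires simultaneous dosing, that the rules contradict each other, or that the stop is void. The documents support none of these. The stop works whenever patient 3 comes later, in cohorts larger than 3, and for replacement patients (Section 3.3.5). What remains is that its protection in a 3-patient cohort is left to recruitment timing.

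The second reply is that other safeguards narrow the gap, and they do:

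- The Day 4 review does look at the DLE eye data, and its minutes go to all investigators (Section 3.1).
- The Safety Monitoring Committee (SMC) can judge whether further enrolment is appropriate (Sections 1.4.2.4 and 8.7).
- Some DLEs would be serious, since an event is serious if it "Is deemed serious for any other reason if it is an important medical event" (Section 5.2.7.1.2), and the sponsor's Always Serious list may add more (Section 5.2.7.1.3). Those would close the gate.
- Section 3.3.4.3 interrupts enrolment after one related serious reaction "or two severe adverse reactions in two different patients".

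None of these requires patient 3 to wait after DLEs that are neither serious nor severe.

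Third, a single sentinel followed by the rest is a recognised design, which Section 1.4.2.4 ties to EMA and ICH guidance, and Section 3.2 values rapid dose finding. That argues against a fixed stagger in every cohort, but not against a conditional hold.

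**Conclusion.** The point holds as a low-severity gap in the plan as written: following the stated release rule can defeat the stated stopping rule in a cohort of exactly 3. The effect is bounded at one patient per such cohort. The chance that the stop's condition is met is at most 0.01% to 16% across the protocol's scenarios at the inferred top dose, and about 3.0% under its prior after two clean cohorts. The real gap is smaller: patient 1's DLE must pass the serious-event gate, Section 3.3.4.3 must not act first, and patient 3 must already have been dosed.

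The figures assume independent patients, the third column as the top dose and, for the 3.0% only, a reference dose of 3. Figure 3.1:1, the SMC charter and the Always Serious list were not available and may narrow the gap further.

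A reader might also infer that trial patients were harmed or are still at risk. The documents do not support that: protocol Section 1.2 reports no DLEs in the twelve treated SRD patients, and SAP Section 6.1 gives 12 as the final SRD enrolment. The point matters for the record and for any reuse of this design.

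**What to change.** In protocol Section 3.1, after the sentence that releases the remaining two patients, add:

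*If, when patient 3 is due, patient 1 has had a DLE, or has an ocular sign that meets a grade or pressure threshold of Section 5.2.1 but not yet its duration, patient 3 is not dosed until patient 2's DLE status is known (Visit 4, Day 8).*

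Patient 2 is still dosed, because the stop needs two DLEs. All other cohorts keep their current timing.

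**Cost.** One sentence and no extra patients. In triggered cohorts only, patient 3 waits about 7 days (5 to 9, given the Visit 4 window of 2 days either side). A repeat-assessment visit may be needed if patient 3's 28-day screening window lapses (Section 6.2.1).

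**Limit.** The hold removes only the share f of the gap in which patient 1's DLE or pending sign is known before patient 3 is dosed. The documents do not give f; it lies between 0 and 1. If f were 0.5 (an assumption), the hold would remove at most half of each bound, for example 7.8% × 0.5 = 3.9% in scenario 3 and 16% × 0.5 = 8.0% in scenario 6. A DLE in patient 1 that first appears after patient 3 is dosed stays uncovered. Closing that would need a fixed stagger in every cohort, which I do not propose.

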### 3.2                      DISCUSSION OF TRIAL DESIGN, INCLUDING THE CHOICE OF CONTROL GROUP(S)

This trial is designed to confirm that the MFD can be used for further testing in phase IIb trials. The trial consists of separate SRD and MD parts. The SRD dose escalation part is included and was designed with the goal to minimize the number of patients exposed to sub-therapeutic doses while on the other hand preserving safety and rapid dose finding. This part of the trial will be done in patients with DMI because IVT injections in healthy volunteers would not be considered appropriate. Whilst the drug may not benefit the participant directly during the trial, DMI is a chronic and bilateral disease. Therefore, if this trial leads to the approval of a treatment for DMI, the participant's other eye as well as the eye treated in the study may benefit from the treatment in the future. The worse seeing eye of the participant will be treated. As mentioned previously, risks are low but if the eye under trial treatment comes to harm, the impact on the patient will be less as the participants' visual function is driven by the better seeing eye. Dose escalation and cohort size will be decided by the SMC, guided by a BLRM with overdose control. An EWOC design will increase the chance of treating patients at efficacious doses while reducing the risk of overdosing. The use of BLRM for Phase I studies has also been advocated by the European Medicines Agency (EMA)

guideline on small populations [[R07-4856](#)] and by the Food and Drug Administration (FDA) [[R13-4881](#)].

One MD cohort (3 injections in 4-weekly intervals) will be included after the SRD part. Patients will be randomized either to active treatment group or to sham control group (ratio 2:1).

This part of the trial will generate additional safety data after multiple dosing and allow for exploration of the time course and durability of treatment effects. These data will further support the definition of the injection frequency and intervals in later studies.

### **3.3 SELECTION OF TRIAL POPULATION**

This trial will recruit approximately 45 patients in total; up to 15 patients in the SRD part (depending on the dose escalation) and up to 30 patients in the MD part. In the MD part, patients will be randomized to receive either IVT injection or sham injection.

Screening of patients for this trial is competitive, i.e. screening for the trial will stop at all sites at the same time once a sufficient number of patients has been screened. Investigators will be notified about screening completion and will then not be allowed to screen additional patients for this trial.

A log of all patients enrolled into the trial (i.e. who have signed informed consent) will be maintained in the Investigator Site File (ISF) at the investigational site irrespective of whether they have been treated with investigational drug or not.

Patients who do not fulfil all eligibility criteria for a reason that later resolves and allows eligibility criteria to be met after the initial screening visit, can be re-screened up to one time. Please refer to Section [6.2.1](#) for further details.

If a patient is entered in error (does not meet all inclusion criteria or meets one or more exclusion criteria on the day of enrolment), the sponsor has to be contacted immediately.

It is planned to conduct the trial in up to 3-5 countries and at approximately 20 sites.

#### **3.3.1 Main diagnosis for trial entry**

Patients to be included are pan-retinal photo coagulation (PRP) treated proliferative diabetic retinopathy (PDR) patients with diabetic macular ischemia (DMI)

Please refer to Section [8.3.1](#) (Source Documents) for the documentation requirements pertaining to the in-and exclusion criteria.

### 3.3.2 Inclusion criteria

Patients will only be included in the trial if they meet the following criteria:

#### SRD part

1. Pan-retinal photo coagulation treated PDR patients with either no or inactive retinal neovascularization per investigator judgement in the study eye
2. Male or female patients of age  $\geq 18$  years
3. Evidence of DMI per investigator's judgement, defined as any degree of disruption of retinal vascularity in superficial and/or deep retinal plexus in OCTA
4. HbA1c of  $\leq 12.0\%$
5. Best-corrected Visual acuity (VA) in the non-study eye better or equal to the best-corrected VA in the study-eye. If both eyes are eligible and have identical VA the investigator may select the study eye.
6. Best-corrected VA  $\leq 55$  letters (20/80) or worse for SRD
7. Women of childbearing potential (WOCBP) and men able to father a child must be ready and able to use two methods of contraception with at least one of them being a highly effective methods of birth control per ICH M3 (R2) that result in a low failure rate of less than 1% per year when used consistently and correctly. A list of contraception methods meeting these criteria is provided in the patient information and in Section [4.2.2.3](#)
8. Signed and dated written informed consent in accordance with ICH Harmonized Guideline for Good Clinical Practice (ICH GCP) and local legislation prior to admission to the trial

 A woman is considered of childbearing potential (WOCBP), i.e. fertile, following menarche and until becoming postmenopausal unless permanently sterile. Permanent sterilisation methods include hysterectomy, bilateral salpingectomy and bilateral oophorectomy. Tubal ligation is NOT a method of permanent sterilisation. A postmenopausal state is defined as no menses for 2 years without an alternative medical cause. A high follicle stimulating hormone (FSH) level in the postmenopausal range may be used to confirm a post-menopausal state in women not using hormonal contraception or hormonal replacement therapy. However, in the absence of 2 years of menorrhoea, a single FSH measurement is sufficient.

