## FLOW CHART I (SINGLE RISING DOSE PART)

Trial Periods	Screening Period	Treatment Visit	Follow-up period					End of study
			1	2	3	4	5	
Study Days	Duration 3 to 28 days	Day 1	4	8	15	29	57	99
Study Weeks			Week 1	Week 2	Week 4	Week 8	Week 14	
Time window for visits (days)		none	±1	±2	±2	±3	±7	±7
Informed consent	X							
Demographics	X							
Medical history	X							
Physical examination (including weight)	X	X 				X	X	X
Vital signs	X	X	X	X	X	X	X	X
Laboratory tests	X	X		X	X	X	X	X
12 lead-ECG 	X	X	X			X	X	X
Review of in-/exclusion criteria	X	X						
Dose Assignment		X						
IVT drug administration		X						
Pregnancy test 	X S	X s		X U	X U	X U	X U	X U
PK Sampling 		X	X	X	X	X	X	X
██████████		X			X	X		X
BCVA testing	X	X	X	X	X	X	X	X
SD-OCT	X	X	X	X	X	X	X	X
OCT Angiography	X	X	X	X	X	X	X	X
Fundus Photo	X	X		X	X	X	X	X
Slit lamp and intra-ocular pressure (IOP)	X	X	X	X	X	X	X	X
All AEs/SAEs/AESIs	X	X	X	X	X	X	X	X
Concomitant therapy	X	X	X	X	X	X	X	X
Completion of patient participation 								X

(1) Could be repeated as deemed necessary at investigator's discretion.

- () See Section [5.2.5](#); the ECGs are to be recorded shortly before the PK sampling at the respective time points, see Appendix [10.1](#)
- () Pregnancy testing: serum pregnancy test (XS) is done at screening and on day 1 if more than a week elapsed between screening and day 1, and at the other visits as a reflex when urine testing (XU) is positive.
- () See separate flow chart for PK and [REDACTED] sampling (Appendix [10.1](#)).
- () Completion of patient participation also needs to be completed if the patient withdraws prematurely following assignment to dose level (see Section [3.3.4](#))

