#### Data from clinical studies

Twelve patients have been treated in the SRD part intravitreally with BI 764524 at the time of finalization of CTP version 3. No DLEs, drug-related SAEs or Drug-related AEs were reported.

For a more detailed description of the BI 764524, please refer to the current Investigator's Brochure (IB, [C27076166-01](#)).

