#### **4.2.2.3** Contraception requirements

WOCBP (for the definition please refer to Section [3.3.2](#)) and men able to father a child must use two medically approved methods of birth control throughout the trial (from Visit 1 until End of Study visit) one barrier method (condom), and one highly effective non-barrier method.

Men (trial participant or partner of a trial participant) must use a condom (regardless of vasectomy) if their sexual partner is a WOCBP.

WOCBP (trial participant or partner of a trial participant) must use a highly effective method of birth control per ICH M3 (R2) throughout the trial (from Visit 1 until EOS visit) that results in a low failure rate of less than 1% per year when used consistently and correctly if their sexual partner is a man able to father a child.

- Combined (estrogen and progestogen containing) hormonal birth control that prevents ovulation (oral, intravaginal, transdermal).
- Progestogen-only hormonal birth control that prevents ovulation (oral, injectable, implantable).
- Intrauterine device (IUD) or intrauterine hormone-releasing system (IUS).
- Bilateral tubal occlusion

Or

Patients must abstain from male-female sex if this is defined as being in line with the preferred and usual lifestyle of the patient. Periodic abstinence e.g. calendar, ovulation, symptothermal, post-ovulation methods; declaration of abstinence for the duration of exposure to study drug; and withdrawal are not acceptable.

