**Clinical chemistry**

- Albumin
- Alkaline phosphatase -  $\gamma$ -GT (gamma-glutamyl transferase) reflex test triggered by elevated alkaline phosphatase on two sequential measures
- ALT (alanine aminotransaminase, SGPT)
- AST (aspartate aminotransaminase, SGOT)
- Bicarbonate
- Bilirubin total, fractionated if increased
- Calcium
- Chloride
- Creatinine
- Serum Pregnancy test\*
- Creatine kinase (CK)
- CK-MB, troponin I (reflex tests if CK is elevated)
- Lactate dehydrogenase (LDH)
- Lipase
- Magnesium
- Phosphate
- Potassium
- Protein total
- Sodium
- Urea (BUN)
- LDL/HDL and total cholesterol
- Triglycerides
- TSH
- Folate

---

\*Serum pregnancy test at screening and at visit 2 as well as confirmation of positive urine pregnancy test (only for WOCBP)

Table 5.2.4: 2 Safety laboratory parameters – urine

---

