#### Human urine chorionic gonadotropin (HCG)\*

---

\*Pregnancy testing (HCG, urine): performed on-site, see flow chart I and flow chart II (only for WOCBP)

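### The last sentence of the childbearing-potential footnote, in both parts, can be read as letting one FSH value override the footnote's own 2-year definition of menopause (minor wording error).

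*Protocol*

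**What the plan says.** Footnote 1 to the inclusion criteria (Protocol Section 3.3.2) appears in both the SRD and the MD part and makes three statements about menopause in this order.

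1. The definition: "A postmenopausal state is defined as no menses for 2 years without an alternative medical cause".
2. The role of FSH: a high value in the postmenopausal range "may be used to confirm a post-menopausal state in women not using hormonal contraception or hormonal replacement therapy".
3. The closing sentence: "However, in the absence of 2 years of menorrhoea, a single FSH measurement is sufficient".

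The classification is used elsewhere in the protocol. Section 4.2.2.3 refers back to Section 3.3.2 for the definition and says that women of childbearing potential "must use two medically approved methods of birth control throughout the trial". The footnote to Table 5.2.4: 1 restricts blood testing to the same group ("Serum pregnancy test at screening and at visit 2 as well as confirmation of positive urine pregnancy test (only for WOCBP"), and the footnote to Table 5.2.4: 2 does the same for the urine test.

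**The concern.** The third statement does not fit the first two. A definition is given, FSH is allowed to confirm that the definition is met, and then one FSH value appears to be enough for a woman who does not meet it. A site that follows the closing sentence in this sense could class a woman with less than two years without menses as postmenopausal. She would then have no contraception duty and no scheduled pregnancy test in a first-in-human trial. The issue is participant safety and a consistent eligibility rule; no statistical result is at stake.

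**Working it through.** The plan states no figure on this point, so the check compares the text under each reading and then counts the tests that depend on the classification.

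**The two readings of the closing sentence**

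| Reading of *menorrhoea* | What the sentence then says | Fit with the rest of the footnote |
|---|---|---|
| (a) slip for amenorrhoea | Without two years of amenorrhoea, one FSH value is enough | Contradicts the definition, and goes beyond confirming |
| (b) literally menses | After two years without menses, one FSH value is enough | Consistent, but she already meets the definition, so the sentence adds nothing and *However* contrasts with nothing |

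Reading (a) gives *However* a function, which makes it the more natural one. No other section resolves the point. The readable amendment log does not mention the sentence, although nearby text was revised: Section 11.1 records a new exclusion of pregnant and lactating women after authority feedback, and Section 11.2 records an edit to the contraception wording.

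**Tests that depend on the classification (reading (a) only)**

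Inputs: Flow Charts I and II. The serum test "is done at screening and on day 1 if more than a week elapsed between screening and day 1"; urine tests follow at five later visits in each part.

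- Screening serum: 1
- Day 1 serum: 0 or 1
- Urine: 5
- Total: 1 + 0 + 5 = 6, or 1 + 1 + 5 = 7 per woman

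**Tests that could still be restored, SRD part**

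- Protocol Section 1.2: "Twelve patients have been treated in the SRD part intravitreally with BI 764524 at the time of finalization of CTP version 3". SAP Section 6.1 gives 12 as the total enrolled in the SRD part, so all had been dosed by then.
- Assumption: version 3 is Global Amendment 2, dated 28 Sep 2021, because the Amendment 1 log calls its own text version 2.
- Latest end of study: Day 99 + 7 = Day 106, which is 105 days after dosing. 28 Sep 2021 + 105 days = 11 Jan 2022.
- From 11 Jan 2022 to the current protocol date of 07 Oct 2022 is 269 days.
- Outstanding SRD tests: 0.

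**Tests that could still be restored, MD part**

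Urine tests fall on Days 29, 57, 85, 113 and 155.

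| Completed up to | Urine tests remaining |
|---|---|
| Day 1 | 5 |
| Day 29 | 4 |
| Day 57 (third injection) | 3 |
| Day 85 | 2 |
| Day 113 | 1 |
| Day 155 (end of study) | 0 |

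SAP Section 6.1 gives 32 MD patients. The upper limit is the number of women among them who are still in follow-up; the documents do not give it.

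**The case against.** The strongest reply is that the documents show an unclear word and no proven error. Taken literally, the sentence agrees with the definition and harms nobody. Even with amenorrhoea substituted, the sponsor may have intended FSH as an alternative route for women off hormones, and a stated exception need not contradict the rule before it. On that view, writing *not sufficient* reverses the sentence without evidence of intent.

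The practical effect is also narrow. Recruitment is complete according to SAP Section 6.1. FSH is not in the protocol's laboratory tables, so no scheduled procedure produces the value. The exclusion of pregnant women (Section 3.3.3), withdrawal for pregnancy (Section 3.3.4.1) and 24-hour reporting of exposure in pregnancy (Section 5.2.7.2.3) all apply whatever the classification. Section 1.4.2 also anticipates very low systemic exposure.

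Much of this stands. The intended meaning cannot be proved from the documents, the number affected may be zero, and the other safeguards are real. They limit the size of the problem without removing the defect. An intended exception would still clash with a footnote that presents the two years as the definition and FSH as confirmation. Under every reading, the sentence is contradictory or redundant.

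**Conclusion.** The concern holds, as a minor wording error in an eligibility definition with safety consequences. Under reading (b) its size is zero. Under reading (a), a possibly fertile woman could lose the contraception duty and up to 6 or 7 pregnancy tests; how many women that concerns is unknown and may be none. Of those tests, none can be outstanding in the SRD part, and at most 5 urine tests per woman can be outstanding in the MD part, falling to 0 at end of study.

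The conclusion rests on two assumptions: that *menorrhoea* stands for amenorrhoea, and, for the SRD count, that protocol version 3 is Amendment 2. Endpoints, sample size and analysis are untouched.

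**What to change.** In the closing sentence of footnote 1, in both parts, replace *menorrhoea* with *amenorrhoea* and *sufficient* with *not sufficient*. This agrees with the footnote's own definition, gives *However* a function and errs toward protection. If the sponsor did intend FSH as an alternative criterion, the definition itself should say so openly.

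Then confirm that no woman still in MD follow-up was classed as postmenopausal on FSH alone. If one was, apply the contraception requirement and the remaining urine tests up to end of study.

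The cost is one phrase in two footnotes and one check limited to women among the 32 MD patients who are still in follow-up.
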